9.4.2 Secondary outcomes

The secondary outcomes are measurement of patient symptoms as measured by the validated Sino-Nasal Outcomes Test (SNOT-22) and physical exam endoscopic findings as documented by Lund-Kennedy endoscopic scoring system

9.5 Data Analyses

Statistical Methods

Continuous patient characters will be summarized with means and standard deviations for features that are approximately normally distributed and with medians, interquartile ranges, and ranges otherwise. Categorical features will be summarized with frequency counts and percentages.

Primary endpoint:

Number and proportion of patients who developed antibiotic resistance organism will be summarized. 95% confidence intervals will be provided for the proportion.

Secondary endpoint:

1) SNOT-22 symptom scores and Lund-Kennedy endoscopic exam score will be summarized as mean (standard deviation) and median (range).

2). Definition of adherence to study intervention will be to complete 25 of 28 days of topical antibiotics and attend the pre-intervention / enrollment visit as well as the post-intervention assessment visit. Number and proportion of patients with adherence will be reported.

3) Audiometric data will be summarized as a mean (standard deviation) and median (range)

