1.1 Primary Objective

The primary objective is to describe the results of antibiotic resistant organisms after the use of topical antibiotics in the treatment of chronic rhinosinusitis.

The secondary objectives are to investigate 1) the effects of topical antibiotics on patient symptoms as measured by the validated Sino-Nasal Outcomes Test (SNOT-22) and physical exam endoscopic findings as documented by Lund-Kennedy endoscopic scoring system. 2) the adherence to study intervention

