3 STUDY DESIGN

This is a prospective, pilot study to investigate the presence or absence of antibiotic resistant organisms after treatment of chronic rhinosinusitis with topical antibiotics. In addition, therapeutic effects of the topical antibiotics will be investigated via assessment of patient symptoms, and physical exam endoscopic findings.

There will be 1 study group with 20 patients.

The patients will first undergo pre-intervention assessment in the outpatient setting. This will occur in the Department of Otorhinolaryngology on the 12th floor of the Gonda building in Rochester, MN with one of the staff rhinologists. Patients will be selected to participate if they have active mucopurulence on their endoscopic examination. The assessment will consist of 1) obtaining a nasal swab of mucopurulence from the affected sinus to be sent for gram stain, culture and sensitivity, 2) assessment of patient symptom severity score as measured by the self-administered Sino-Nasal Outcomes Test (SNOT-22) survey, and 3) assessment of patient physical exam as evaluated by rigid nasal endoscopy and documented in Lund-Kennedy endoscopic findings form.

The study intervention is the administration of culture directed topical antibiotics over 28 days. These antibiotics will prescribed to the patient in capsule form as compounded by the Mayo Clinic pharmacy, or suitable licensed compounding pharmacy. One capsule will subsequently be added to a nasal saline irrigation bottle, and the patient will administer this irrigation to him or herself in the usual fashion twice per day.

- The dosages of the antibiotic capsules were determined by the Mayo Clinic pharmacy team with input from infectious disease, based upon available published data, and will be as follows, dissolved in a standard 240mL saline irrigation rinse
 - Mupirocin: 30 mg
 - Tobramycin: 192 mg
 - Gentamicin: 192 mg
 - Levofloxacin: 250mg

After the completion of the study intervention (within 21 days), the patient will undergo post-intervention assessment in the outpatient setting, again in the Department of Otorhinolaryngology with one of the staff rhinologists. The patient will again be assessed with 1) nasal swab from the affected sinus sent for gram stain, culture and sensitivity 2) SNOT-22 symptom scores and 3) Lund-Kennedy endoscopic exam scores.

SELECTION AND ENROLLMENT OF PARTICIPANTS 4

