5.2 Handling of Study Interventions

After completion of the intervention, the patient will present for post-intervention assessment in the Department of Otorhinolaryngology on the 12th floor of the Gonda building in Rochester, MN with one of the staff rhinologists. This assessment will be exactly the same as the pre-intervention assessment. Specifically, this assessment will consist of 1) obtaining a nasal swab of mucopurulence from the affected sinus to be sent for gram stain, culture and sensitivity, 2) assessment of patient symptom severity score as measured by the self-administered Sino-Nasal Outcomes Test (SNOT-22) survey, and 3) assessment of patient physical exam as evaluated by rigid nasal endoscopy and documented in Lund-Kennedy endoscopic findings form.

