6 STUDY PROCEDURES

6.1 Schedule of Evaluations

Pre-Intervention assessment: to be completed before starting intervention

- Nasal swab: Obtain swab from affected sinus and send for gram stain, culture and sensitivity
- Patient symptom evaluation as assessed by SNOT-22 symptom scores
- Patient endoscopic physical exam as assessed by Lund-Kennedy endoscopic exam scores. Documentation photos will also be obtained with two endoscopic photos per side, one from the head of the inferior turbinate into the nasal cavity and one from the head of the middle turbinate towards the middle meatus.

Post-Intervention assessment: to occur after the completion of the 28 days of intervention with topical antibiotics

- Nasal swab: Obtain swab from affected sinus and send for gram stain, culture and sensitivity
- Patient symptom evaluation as assessed by SNOT-22 symptom scores
- Patient endoscopic physical exam as assessed by Lund-Kennedy endoscopic exam scores. Documentation photos will also be obtained with two endoscopic photos per side, one from the head of the inferior turbinate into the nasal cavity and one from the head of the middle turbinate towards the middle meatus.

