10 DATA COLLECTION AND QUALITY ASSURANCE

10.1 Data Collection Forms

Information will be collected on Case Report Forms (CRFs) by study staff. Participant CRFs will be kept in a locked cabinet in the Department of Otorhinolaryngology and only study staff will have access to this cabinet to maintain confidentiality of participant records.

Data Management

All data is checked for completeness and for accuracy on data ranges.

Data collection forms will be organized in the following categories:

-Enrollment / Pre-intervention assessment

-Post-intervention assessment

Data will be collected and stored using excel file.

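### SNOT-22 and Lund-Kennedy are measured before and after treatment in the same patients, but sections 9.4.2 and 9.5 plan no within-patient change and no interval for it

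*Combined protocol and SAP*

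**What the plan says.** All references are to the combined protocol and SAP.

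- **Objective.** Section 1.1 sets as a secondary objective "the effects of topical antibiotics on patient symptoms as measured by the validated Sino-Nasal Outcomes Test (SNOT-22"), together with endoscopic findings on the Lund-Kennedy system.
- **Measurement.** Section 3 has both scales scored before treatment and lists "SNOT-22 symptom scores and 3) Lund-Kennedy endoscopic exam scores" again at the post-treatment visit. Section 5.2 says of the second visit: "This assessment will be exactly the same as the pre-intervention assessment". Section 6.1 lists the same item under both assessments: "Patient symptom evaluation as assessed by SNOT-22 symptom scores".
- **Outcome definition.** Section 9.4.2 reads: "The secondary outcomes are measurement of patient symptoms as measured by the validated Sino-Nasal Outcomes Test (SNOT-22"), and adds the endoscopic score. It names no time point and no change from baseline.
- **Analysis.** Section 9.5 reads: "SNOT-22 symptom scores and Lund-Kennedy endoscopic exam score will be summarized as mean (standard deviation) and median (range"). It does not say which visit or visits are summarised.
- **Intervals.** The only interval in section 9.5 belongs to the primary endpoint: "95% confidence intervals will be provided for the proportion".
- **Data layout.** Section 10.1 groups the forms into "Enrollment / Pre-intervention assessment" and a post-intervention counterpart, so a summary by visit is the natural reading of section 9.5, though it is not stated.

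**The concern.** The study has one arm and no control. An objective about effects on the two scores can therefore be addressed only by describing how each patient changed. The data are collected in pairs for that purpose, but the analysis text treats the scores as if pairing did not matter.

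A by-visit table of mean (SD) and median (range) leaves three gaps:

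- **Precision.** The spread of the individual changes, and so the uncertainty of the mean change, cannot be derived from the two visit SDs.
- **Median change.** The difference between two visit medians is not, in general, the median of the differences.
- **Who is in each row.** The difference of the visit means equals the mean change only if both rows contain the same patients. No count of pairs is planned, and section 5.4 speaks of using the endpoints that are available.

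Section 9.2 says the pilot is meant to describe results and to gather data for a larger study. The SD of within-patient change is a standard planning input if that study uses change from baseline, and the planned table would not contain it.

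**Working it through.** **No figure to reproduce.** The documents state no SD, pre-post correlation, target change or precision for either scale, and section 9.2 says that no sample size calculation is required. The check therefore asks what a by-visit table would let a reader work out.

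**Inputs**

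- n = 20 (Précis and section 3) or n = 40 (sections 9.1 and 9.2). These disagree and need reconciling as a separate matter; both are carried here.
- Confidence level 95%, the level section 9.5 uses for the primary proportion.
- Assumptions not in the documents: complete pairs, equal SDs at the two visits, and a pre-post correlation r of 0, 0.3, 0.5 or 0.7. Results are in units of the single-visit score SD.

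**Formulas**

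1. In general, SD_change² = SD_pre² + SD_post² − 2·r·SD_pre·SD_post. If r ≥ 0, then SD_change ≤ √(SD_pre² + SD_post²). The visit SDs give this upper bound and no more.
2. With equal visit SDs, SD_change = √(2(1 − r)) score SDs.
3. The paired 95% half-width for mean change is t(0.975, n − 1) × SD_change / √n.

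**Numbers put in**

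- n = 20: t(0.975, 19) = 2.093. At r = 0 the half-width is 2.093 × √(2/20) = 0.662.
- n = 40: t(0.975, 39) = 2.0227. At r = 0 the half-width is 2.0227 × √(2/40) = 0.452.
- For other r, multiply by √(1 − r).

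| r | SD of change | Half-width, n = 20 | Half-width, n = 40 | Share of the r = 0 bound |
|---|---|---|---|---|
| 0 | 1.414 | 0.662 | 0.452 | 100% |
| 0.3 | 1.183 | 0.554 | 0.378 | 84% |
| 0.5 | 1.000 | 0.468 | 0.320 | 71% |
| 0.7 | 0.775 | 0.363 | 0.248 | 55% |

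**Reading.** Every row of this table is consistent with the same pair of visit means and SDs. Between r = 0.3 and r = 0.7 the half-width differs by a factor of √(1.4/0.6) = 1.53. If the SD of change is reported, the half-width is fixed at 2.093/√20 = 0.468 SDs of change for 20 patients, or 2.0227/√40 = 0.320 for 40, with no assumption about r.

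**Sensitivity to the comparator.** A reader who treated the two rows as independent samples would use 2n − 2 degrees of freedom and obtain 0.640 (n = 20) or 0.445 (n = 40). Against 0.640, the paired half-widths at r = 0.3, 0.5 and 0.7 are 0.554/0.640 = 87%, 0.468/0.640 = 73% and 0.363/0.640 = 57%. The conclusion does not depend on this choice.

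**The case against.** The strongest reply is that section 9.5 is brief rather than wrong. It names no visit and does not rule out a summary of change. In complete pairs the difference of the visit means is already the mean change. If r is not negative, the visit SDs overstate its uncertainty, so the error is on the safe side. The study is a declared descriptive pilot, these are secondary outcomes, and an interval around uncontrolled change may invite a causal reading. The patient-level data are kept, so the analyst can compute the change later. The figures above are generic and are not in scale points.

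Much of this stands. The mean change is recoverable under complete pairs, nothing is lost for good, and no wrong conclusion is forced. The figures are generic because the documents give no SD or r.

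On missing pairs, section 8 lets patients short of 48 of 56 doses be replaced and not counted, and section 10.3.3 restricts the data to what agrees with the protocol. Both point towards an analysis of patients who finished. Neither guarantees pairs, because replacement is permitted rather than required. The sentence in section 5.4 about available endpoints sits in the adherence text and its reach is unclear, so little weight should rest on it.

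The main point survives even with complete pairs: the visit SDs do not fix the precision of the change. Calling the study descriptive does not answer this, because an SD of change and an interval are themselves description, and the plan already gives an interval for its primary proportion. The risk of a causal reading is met by wording. If the analyst would compute change anyway, stating it in advance costs almost nothing and fixes the definition before results are seen.

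**Conclusion.** The concern holds. No section plans a within-patient change, an SD of change or an interval for SNOT-22 or Lund-Kennedy, although the objective and the visit schedule call for a paired summary. Under complete pairs, equal visit SDs and r between 0.3 and 0.7, the actual 95% half-width would be 84% to 55% of the bound a reader could infer from the visit SDs, and the planned table could not show where in that range it lies. The correlation is an assumption, shown as a range. That the precision is left undetermined does not depend on the value chosen.

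The weight is modest: a reporting improvement that should be made to secondary outcomes of a descriptive pilot.

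**What to change.** In section 9.4.2, define each of the two outcomes as the post-treatment score minus the pre-treatment score in the same patient.

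In section 9.5, for each scale:

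- report pre, post and change in patients with both scores, and state the number of pairs;
- give the mean change, the SD of change and a paired 95% confidence interval;
- give the median (range) of change alongside the summaries already planned;
- report how many patients have no post-treatment score;
- describe the result as change from baseline in one uncontrolled arm, not as an effect of the drug.

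The cost is a few lines of wording in the two sections and a few lines of analysis. Both scores are already collected at both visits and kept in the study data file, so no extra data, visit or patient is needed.

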5.4 Adherence Assessment

Definition of adherence to study intervention will study subject attestation that they completed at least 48 / 56 dosages of nasal saline irrigation with topical antibiotic and presentation for one post-intervention assessment. Patient will record topical antibiotic use in a daily log. This log will be used by the investigators to assess adherence. These available endpoints will be taken and incorporated into analysis.

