9.2 Sample Size and Randomization

We propose enrolling 40 patients in this study. Since this study is a pilot study where we aim to describe the results and collect data for future larger study, sample size calculation is not required.

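### Adherence combines doses taken with attendance at the follow-up visit, and no separate report of dosing adherence or retention is specified

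*Combined protocol and SAP*

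**What the plan says.** Section 1.1 lists "the adherence to study intervention" as the second of the secondary objectives. Adherence is defined in two places.

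- **Section 5.4** requires the patient's attestation of having "completed at least 48 / 56 dosages of nasal saline irrigation with topical antibiotic and presentation for one post-intervention assessment". The data source is a diary: "Patient will record topical antibiotic use in a daily log. This log will be used by the investigators to assess adherence". The section closes by saying, without detail, that the available endpoints will enter the analysis.
- **Section 9.5**, secondary endpoint 2, requires 25 of 28 days of treatment and that the patient "attend the pre-intervention / enrollment visit as well as the post-intervention assessment visit". The only planned output is this: "Number and proportion of patients with adherence will be reported".

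Two other sections bear on the figure. Section 8 allows replacement of participants who discontinue early or who fall short of 48 of 56 doses, and leaves those replaced out of the count. Section 9.2 states that one aim of the pilot is to "collect data for future larger study".

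**The concern.** The objective concerns adherence to the intervention, and the intervention is the antibiotic rinse. Both definitions add a second event, return to the clinic, so the planned proportion is the joint rate of dosing and attendance. A patient who took every dose but did not return is scored the same as one who abandoned the rinses.

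A larger study would use the two components differently. Dosing adherence shows whether the regimen is workable. Retention is the rate at which the primary outcome can be observed at all, because the outcome swab is taken at the post-intervention visit. It would therefore drive any allowance for loss to follow-up. If the composite is low, it does not show which component failed.

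This is separate from the disagreement between the 48/56-dose and 25/28-day thresholds. Settling that would leave the attendance condition in both definitions.

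**Working it through.** The plan states no expected adherence, attendance or dropout rate, so there is no figure of its own to reproduce. All rates below are assumed.

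**1. The fully dosed patient who misses follow-up.** Two doses a day for 28 days is 2 × 28 = 56 doses.

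| Condition | Section 5.4 | Section 9.5 |
|---|---|---|
| Dosing | 56 ≥ 48 (threshold 48/56 = 85.7%): met | 28 ≥ 25 days (threshold 25/28 = 89.3%): met |
| Enrolment visit | not required | met by every participant |
| Post-intervention visit | not met | not met |
| Scored | non-adherent | non-adherent |

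The enrolment-visit condition does no work: sections 5.1 and 6.2.2 place enrolment and the pre-intervention assessment at that visit.

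**2. What the composite can show.** Let d be the proportion meeting the dosing condition and v the proportion attending follow-up. The composite c satisfies max(0, d + v − 1) ≤ c ≤ min(d, v), and equals d × v if the two are independent.

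- d = 0.90, v = 0.80: lower bound 0.90 + 0.80 − 1 = 0.70; upper bound 0.80; independent 0.90 × 0.80 = 0.72. That is 14 to 16 of 20 patients, or 28 to 32 of 40 (the documents give both sample sizes).
- d = 0.90, v = 0.90: lower bound 0.80; upper bound 0.90; independent 0.81.

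**3. It cannot be reversed.** A reported c = 0.80 is compatible with d anywhere from 0.80 to 1.00 and v anywhere from 0.80 to 1.00. At one extreme (d = 1.00, v = 0.80), a later study would need 1/0.80 = 1.25 times the enrolment to cover loss to follow-up. At the other (d = 0.80, v = 1.00), it would need no such allowance. Sampling error adds to this: the exact 95% interval is 56% to 94% for 16/20 and 64% to 91% for 32/40.

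**4. Effect of replacement under section 8.** Suppose that everyone below the dosing threshold is replaced, one threshold applies throughout, and attendance does not depend on dosing. The counted patients then all meet the dosing condition, and the composite equals v. Take d = 0.90 among all who start treatment:

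| Assumed v | Composite, no replacement (0.90 × v) | Composite, full replacement (v) | Full replacement compared with d = 0.90 |
|---|---|---|---|
| 0.80 | 0.72 | 0.80 | below |
| 0.95 | 0.855 | 0.95 | above |

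So the reported figure can fall on either side of the dosing rate.

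**The case against.** **The figures can be derived anyway.** A reader might infer that the pilot will be unable to give dosing adherence or retention. The documents do not support that. The daily log holds dosing data, and the closing sentence of 5.4 does not confine the analysis to the composite. The swab, SNOT-22 and Lund-Kennedy score are all due at the one follow-up visit, so the number with post-treatment data would roughly show retention, subject to replacement. This stands: separate reporting is unspecified, not impossible. Even so, 9.5 names only the composite, and a log that is never collected cannot be recovered at analysis.

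**The rule understates adherence.** This too is a tempting inference, and it goes too far. The attendance condition lowers the proportion, but replacement under section 8 raises it. Section 8 also covers early discontinuation, so a patient who does not return might be dropped and not scored non-adherent. The text does not settle this.

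**Attendance may be a condition of measurement.** Section 10.1 provides forms only for the pre- and post-intervention assessments, and no return of the log outside the visit is described. For many non-attenders the doses taken may simply be unknown. That is fair, but unknown dosing should be shown as unknown and not counted as failure.

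**A dosed-and-assessed definition is defensible in a descriptive pilot.** It is, as a description of completers. It does not match an objective worded as adherence to the intervention, and reporting the components loses nothing.

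**Conclusion.** The point holds as a reporting defect in a descriptive secondary endpoint. Both definitions make post-intervention attendance part of adherence, 9.5 plans only the joint proportion, and that proportion cannot be separated into the two quantities a larger study needs. The primary proportion is not affected, and the 20 versus 40 discrepancy in sample size does not change the argument.

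The size is unknown, because the documents give no rates. The range of 70% to 80% for 90% dosing and 80% attendance is an illustration. The 72% within it also assumes independence, which is doubtful if patients who stop rinsing are also less likely to return. No net direction of bias can be claimed while section 8 allows patients with low dosing to leave the denominator.

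**What to change.** Remove visit attendance from the adherence definition in 5.4 and 9.5. Replace item 2 of the secondary endpoints in 9.5 with two results, both among all patients who start treatment, including any later replaced:

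- **(a) Dosing:** doses taken out of 56 from the daily log, as mean (SD) and median (range), with the number and proportion meeting one dosing threshold. The 48/56-dose and 25/28-day passages must first be reconciled. Show patients who return no log as dosing unknown.
- **(b) Retention:** number and proportion attending the post-intervention visit.

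State in section 8 that replaced patients stay in this denominator. Without that sentence, changes to 5.4 and 9.5 alone would not deliver it.

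The cost is wording in three sections and one more table row. Collecting logs by telephone or electronically from patients who do not attend is optional. It would take some effort and would reduce the number with dosing unknown.

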Topical Antibiotics in Chronic Rhinosinusitis

NCT03673956

August 26, 2018

Topical Antibiotics in Chronic Rhinosinusitis

v3 8-26-18

i

PRÉCIS

Study Title

Topical Antibiotics in Chronic Rhinosinusitis

Objective

The primary objective is to show that the use of topical antibiotics in the treatment of chronic rhinosinusitis does not lead to antibiotic resistant organisms. The secondary objectives are to investigate the effects of topical antibiotics on patient symptoms as measured by the validated Sino-Nasal Outcomes Test (SNOT-22) and physical exam endoscopic findings as documented by Lund-Kennedy endoscopic scoring system.

Design and Outcomes

This is a prospective pilot study to evaluate development of antibiotic resistance in patients with chronic rhinosinusitis who are being treated with topical antibiotics.

Interventions and Duration

Intervention includes 28 days of culture directed antibiotic therapy with one of the following four topical antibiotics: Tobramycin, Mupirocin, Gentamicin or Levofloxacin

Sample Size and Population

There will be 20 participants total in the study and they will all receive the intervention.

STUDY TEAM ROSTER

Principal Investigator: [name]

[name], MD

[contact] [contact]

Co-Investigators:

[name] [contact]

[name] [contact]

Study Team:

[name] [contact]

[name], MS Biostatistician Phone:

[name], CCRP Research Coordinator

[name] Research Coordinator

Phone: Pager:

1 STUDY OBJECTIVES

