2.2 Study Rationale

The interventional regimen is as follows.

Patient will undergo pre-intervention nasal swab from the affected sinus that will be sent for gram stain and bacterial culture and sensitivities.

If pathogen identified in the bacterial culture is pseudomonas aeruginosa, topical tobramycin or gentamycin will be assigned as first line agent pending culture profiles and cost factors. If the sensitivities show resistance to both tobramycin and gentamycin, then levofloxacin will be prescribed.

If the pathogen identified in the bacterial culture is other than pseudomonas aeruginosa, mupirocin will be prescribed. If the pathogen shows resistance to mupirocin, then the patient will be prescribed one of the other three antibiotics will be prescribed pending culture profiles and cost factors

The patient will use the topical antibiotic twice a day for 28 days. This will be accomplished by first proceeding with their normal nasal rinse regimen as prescribed by their physician (this may include saline alone, or saline with budesonide). Twice per day, at the end of each regimen, they perform one additional nasal saline rinse using the Neil Med sinus rinse bottle in the manner outlined on the packaging instructions. However, with this last additional nasal saline rinse, they will open their antibiotic capsule and drop the contents into the rinse bottle prior to rinsing.

Known and potential risks are as follows:

Potential risks of nasal saline irrigation is stinging sensation and burning Potential risks of filling the nasal saline irrigation rinse bottle with water that is too hot is mucosal burns

Potential risks of topical antibiotic administration include local pruritis and inflammation Potential risks of selection antibiotic resistant organisms. Potential risk for hearing loss

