7.3 Adverse Events and Serious Adverse Events

An **adverse event (AE)** is generally defined as any unfavorable and unintended diagnosis, symptom, sign (including an abnormal laboratory finding), syndrome or disease which either occurs during the study, having been absent at baseline, or if present at baseline, appears to worsen. Adverse events are to be recorded regardless of their relationship to the study intervention.

A serious adverse event (SAE) is generally defined as any untoward medical occurrence that results in death, is life threatening, requires inpatient hospitalization or prolongation of existing hospitalization, results in persistent or significant disability/incapacity, or is a congenital anomaly.

No serious adverse event out of character with nasal irrigations is expected.

Adverse events captured during interval clinical visit are captured as unsolicited events, but if patient reports by calling PI directly using number on the consent form it will be captured as a solicited event. The events will be recorded as such so that there are no double collection systems.

If there are any adverse events or serious adverse events reported by the patient to the co-investigators at any point post-interventional procedure throughout the study, the Principal Investigator will be notified within 24 hours.

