7.4 Reporting Procedures

If there are any adverse events or serious adverse events reported by the patient to the co-investigators at any point (post-interventional procedure) throughout the study, the Principal Investigator will be notified within 24 hours. The co-investigator will record the occurrence in the patient's research file within 24 hours of report of the incident.

Decision of relatedness and severity will be made by the Principle Investigator.

Details of the adverse event will be maintained in the Reportable Event Tracking Log for this study.

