9.3 Interim analyses and Stopping Rules

Safety findings that would temporarily suspend enrollment and/or study intervention until a safety review is convened (*either routine or ad hoc*) to determine whether the study should continue per protocol, proceed with caution, be further investigated, be discontinued, or be modified and then proceed are as follows:

-Number of SAEs overall

-Number of occurrences of a particular type of SAE

-Severe AEs/reactions

-Increased frequency of events

Such findings are presented to the Data and Safety Monitoring Board (DSMB) statistician

to review the events by group to determine whether there are statistical as well as clinical concerns. The statistician reports his findings to a closed session of the DSMB (or to the Safety Officer and/or NIA.) The findings are used to determine what steps will be taken.

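### Hearing loss is a named risk, but the planned audiometric summary (9.5, item 3) does not show how many patients worsened or on which antibiotic

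*Combined protocol and SAP*

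**What the plan says.** Section 2.2 ends its list of known and potential risks with "Potential risk for hearing loss". Section 9.5, third item under the secondary endpoint, gives the whole audiometric analysis: "Audiometric data will be summarized as a mean (standard deviation) and median (range". It names no ear or frequency, no change from baseline, no criterion for worsening and no split by drug.

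The same section handles the primary endpoint patient by patient: "Number and proportion of patients who developed antibiotic resistance organism will be summarized", with a 95% confidence interval. Adherence also gets a number and proportion.

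Other sections can pick up a hearing loss. The adverse event definition in 7.3 covers a sign that is new, "or if present at baseline, appears to worsen". Section 7.4 adds: "Details of the adverse event will be maintained in the Reportable Event Tracking Log for this study". One of the triggers for safety review in 9.3 is "Number of occurrences of a particular type of SAE".

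The assessments in section 3, section 5.2 and the schedule in 6.1 consist of a swab, SNOT-22 and endoscopy. Audiometry is in none of them. Section 5.2 says of the post-treatment visit: "This assessment will be exactly the same as the pre-intervention assessment".

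On size, the Précis says "There will be 20 participants total in the study", while 9.1 and 9.2 say 40. Both are used below.

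**The concern.** A hearing loss from treatment would be an event in individual patients. The useful descriptive facts are how many of those tested worsened, by how much, and on which drug. Four antibiotics are pooled in one group, and a mean, SD, median and range of the pooled values give neither the count nor the drug.

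The wording also leaves open what is summarised. With raw values in adults aged 18 to 80 (4.1), the maximum may belong to someone who already heard poorly before treatment, so a new loss in another patient can lie inside the range.

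What is at stake is how useful the pilot is to its successor. Section 9.2 gives the aim as describing results and collecting data for a larger study, and that study would want the count and the drug. The primary endpoint is not affected.

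**Working it through.** The plan gives no hearing figure to reproduce. That the count and the drug are missing follows from the text alone. The arithmetic below only shows how much the planned summary could still reveal.

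**Inputs.** From the documents: n = 20 (Précis, section 3) or 40 (9.1, 9.2). Assumed, because the documents give no dB values: a loss of 20 or 30 dB in k = 1 or 2 patients, between-patient SD 10-20 dB, and independent retest error with SD 5 dB at each visit. The SD of a change is then √(5² + 5²) = 7.07 dB. The SD of a single raw value is √(SD² + 5²), which is 11.2 to 20.6 dB.

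**1. Does an affected patient set the maximum?** With normal errors, this is the probability that the largest of the k shifted values exceeds the largest of the n − k unshifted ones.

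| Loss | n | k | Raw values (between-patient SD 20 to 10) | Changes |
|---|---|---|---|---|
| 20 dB | 20 | 1 | 22-48% | 81% |
| 20 dB | 20 | 2 | 38-71% | 95% |
| 20 dB | 40 | 1 | 14-37% | 73% |
| 20 dB | 40 | 2 | 26-59% | 91% |
| 30 dB | 20 | 1 | 37-77% | 98% |
| 30 dB | 40 | 1 | 27-69% | 97% |

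**2. Does the mean move visibly?** The shift is loss × k/n, from 20 × 1/40 = 0.5 dB to 30 × 2/20 = 3.0 dB.

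- Raw values: the standard error runs from √(125/20) = 2.50 to √(425/20) = 4.61 dB at n = 20, and from √(125/40) = 1.77 to √(425/40) = 3.26 dB at n = 40. The shift is therefore 0.5/3.26 = 0.15 to 3.0/2.50 = 1.20 standard errors.
- Changes: the standard error is 7.07/√20 = 1.58 or 7.07/√40 = 1.12 dB. The shift is 0.5/1.12 = 0.45 to 3.0/1.58 = 1.90 standard errors.

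**3. Can the count be read from a summary of changes?** Take n = 20 with no measurement error, and let one, two or three patients lose 20 dB while the rest do not change. The median is 0 and the range 0 to 20 in all three cases. Only the mean (1.0, 2.0, 3.0 dB) and the SD (4.5, 6.2, 7.3 dB) differ. With retest error, each 1 dB step in the mean is smaller than its standard error of 1.58 dB. The drug cannot be recovered in any case.

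**4. How would a count at 15 dB perform?** With an SD of change of 7.07 dB:

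- Detection of a true 20 dB loss: Φ((20 − 15)/7.07) = Φ(0.71) = 76%, so 24% are missed.
- Detection of a true 30 dB loss: Φ((30 − 15)/7.07) = Φ(2.12) = 98%.
- False positive per unaffected patient: 1 − Φ(15/7.07) = 0.0169. The expected number is 19 × 0.0169 = 0.32, or 39 × 0.0169 = 0.66.

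**5. Precision of the count (Clopper-Pearson 95%).** 1/20: 0.1-24.9%. 2/20: 1.2-31.7%. 1/40: 0.1-13.2%. If only ten patients have paired audiograms, 1/10: 0.3-44.5%.

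**The case against.** The strongest reply is that the larger gap lies elsewhere. Audiometry is absent from the assessments (3, 5.2), the schedule (6.1), the safety parameters (7.1) and the secondary outcomes (9.4.2), so the plan does not assure paired audiograms for anyone. A better summary may cover few patients, and they may be a selected group, for example those with symptoms. This stands. It limits what any proportion can mean, and the fix has to say so.

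A second reply is that adverse event recording already covers hearing. A reader might infer from 9.5 that a hearing loss would go unrecorded. The documents do not support that: 7.3, 7.4 and 9.3 give a route for recording and review. But nothing says that an audiogram shift is to be logged as an event, and 9.5 plans no adverse event table. That route therefore does not put a hearing count into the planned analysis. The missing table affects every harm and is not particular to audiometry.

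A third reply is that this is a small descriptive pilot, that item 3 follows the style used for SNOT-22 and Lund-Kennedy, and that a listing could be made from the data file at reporting time. Much of this stands, and it keeps the point minor. What is gained by writing it down now is a threshold fixed before the data are seen and a commitment to report the drug. The general rule in 9.5 that categorical features get counts does not help, because no categorical hearing variable is defined.

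**Conclusion.** The point holds as a minor, inexpensive improvement. As written, item 3 does not report how many patients worsened or on which antibiotic. This rests on the text and on no assumed figure.

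A reader might go further and infer that the planned summary would hide a hearing loss. The documents do not support that as a general statement, because they do not settle whether raw values or changes are summarised. If changes, the range would usually show the largest loss: 73-81% of trials with one patient losing 20 dB, and 97-98% at 30 dB. If raw values, a loss in one patient may well not show: at 20 dB that patient sets the maximum in only 14-48% of trials. All of these percentages depend on assumed dB inputs and are illustrations, not estimates for this trial.

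Nor would the count give a precise rate. At 20 or 40 patients the interval is wide, and the main gain is the patient listing. Because audiograms are not scheduled, the proportion describes the patients tested, and describes all treated patients only if all were tested.

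**What to change.** Replace item 3 of the secondary endpoint in 9.5 with text such as:

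> For every patient with audiograms before and after treatment, the change from that patient's own baseline will be calculated on one audiometric value per patient (ear and frequencies named before data review). The number and proportion who worsened by at least 15 dB will be reported with an exact 95% confidence interval. Each such patient will be listed with the antibiotic received and the baseline and post-treatment values. Mean (SD) and median (range) of the change will be given as support. The report will state the denominator, the number of treated patients without paired audiograms, and why those tested were tested. The proportion will not be generalised to all treated patients unless audiograms were obtained for all.

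The 15 dB is an example. The team should fix its own threshold in advance, above the retest error of its audiometry.

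The cost is one paragraph, one small table and a listing, with no added visits or patients. The downsides are that a threshold has to be chosen, that some misclassification remains (24% of 20 dB losses missed under the assumed retest error), and that the interval is wide. Scheduling audiograms for everyone before and after treatment would make the proportion interpretable, but it is a separate decision with its own cost.
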